1 SYNOPSIS

Title: Multicenter, Phase 3 Study of Venetoclax and Azacitidine as Maintenance Therapy for Patients with Acute Myeloid Leukemia in First Remission After Conventional Chemotherapy (VIALE-M)

Background and Rationale:

Acute myeloid leukemia (AML) is an aggressive hematologic malignancy typically defined by the World Health Organization (WHO) as a myeloid neoplasm with 20% or more blasts in the peripheral blood or bone marrow. It is the most common form of acute leukemia in adults, with an estimated 19,520 new cases and 10,670 deaths in the United States (US) in 2018. Of all types of leukemia, AML has the lowest survival rate and accounts for the largest number of deaths.

Venetoclax is a selective, potent, orally bioavailable, small molecule inhibitor of B-cell lymphoma (BCL)-2 that restores programmed cell death in cancer cells. Venetoclax was evaluated as a single agent in subjects with relapsed or refractory (R/R) AML or newly diagnosed subjects with AML who were unfit to receive intensive chemotherapy achieving a 19% objective response rate (ORR) with venetoclax monotherapy. Furthermore, ongoing studies in subjects with treatment-naïve AML who were ineligible for intensive chemotherapy reported complete remission (CR) + complete remission with incomplete blood count recovery (CRi) rates of 61% when subjects were treated with venetoclax in combination with hypomethylating agents and 54% in combination with low-dose cytarabine.

For AML patients who are eligible, intensive chemotherapy during induction and consolidation is a standard-of-care treatment. Patients who are fit enough to receive intensive therapy will often achieve remission; however, the majority of these patients will ultimately relapse. The prevention of relapse is a major therapeutic challenge in the treatment of AML and an unmet need remains for AML patients in remission.

This study will determine the recommended Phase 3 dose (RPTD) of venetoclax in combination with azacitidine (AZA; subcutaneous [SC] or intravenous [IV] administration) as maintenance therapy in subjects with AML who have achieved CR or CRi with conventional chemotherapy. This study will also determine the dose of venetoclax in combination with oral AZA (ONUREG®; orally [PO] administered AZA) that can be safely administered (RPTD) as maintenance therapy, and evaluate the safety and efficacy of venetoclax in combination with oral AZA in subjects with AML who have achieved CR or CRi after conventional chemotherapy.

Objectives and Endpoints:

Primary Objective

- Part 1 (Dose Confirmation): To determine the RPTD of venetoclax in combination with AZA as maintenance therapy in subjects with AML who have achieved CR or CRi with conventional induction and consolidation chemotherapy.
- Part 3 (Dose Finding): To determine the RPTD of venetoclax in combination with oral AZA as maintenance therapy in subjects with AML who have achieved CR or CRi with conventional induction and consolidation chemotherapy.

| | Sacandary Objectives |
|---|--|
| | Part 3 (Dose Finding): To characterize the safety, efficacy, pharmacokinetic (PK), and toxicity profiles of venetoclax in combination with oral AZA as maintenance therapy in subjects with AML who have achieved CR or CRi with conventional induction and consolidation chemotherapy. Primary Endpoint Part 1 (Dose Confirmation) The primary endpoint is dose-limiting toxicities (DLTs) of venetoclax in combination with AZA. Part 3 (Dose Finding) The primary endpoint is DLTs of venetoclax in combination with oral AZA. |
| Investigators: | Investigator information on file at AbbVie. |
| Study Sites: | Approximately 250 sites in approximately 17 countries including but not limited to |
| Study Population and Number of Subjects to be Enrolled: | Subjects with AML who have achieved CR or CRi with conventional chemotherapy will be enrolled in the study; as of 26 August 2021, 66 subjects were enrolled in Part 1 (Dose Confirmation); as of 08 September 2022, 46 subjects were enrolled in Part 3 (Dose Finding). |
| Investigational Plan: | This is a Phase 3 multicenter, open-label study of venetoclax in combination with AZA administered PO (oral AZA) to establish the RPTD and safety of the combination in a dose escalation phase (Part 3 [Dose Finding]) followed by a safety expansion component in subjects with AML after first remission resulting from conventional (including both induction and consolidation) chemotherapy. |
| | This study will also have an open-label, dose-confirmation component to establish the recommended dose of venetoclax in combination with AZA (SC or IV) (Part 1 [Dose Confirmation]) in subjects with AML after first remission resulting from conventional (including both induction and consolidation) chemotherapy. |
| | Best supportive care (BSC) and expectant AML management for this patient population according to institutional standards, excluding any AML-directed therapy, is allowed throughout the study. BSC will be determined for each subject by the investigator. |
| | For Part 1, subjects enrolled in the dose-confirmation cohort will receive venetoclax + AZA at the proposed study dose levels. When at least 20 subjects have been treated for at least 28 days, an aggregate review of the toxicity data will occur to determine if the RPTD has been reached. For Part 3 (Dose Finding), subjects enrolled in the dose-escalation cohorts will receive venetoclax + oral AZA at the proposed study dose levels. When the RPTD has been reached, a safety expansion cohort will receive venetoclax + oral AZA at the preliminary RPTD identified from dose-escalation portion of Part 3 (Dose Finding). |

| | Note: Part 2 (open-label, randomized, 2-arm portion of the study with venetoclax + AZA + BSC versus BSC) was removed from Version 5.0 of this protocol. Part 3 (Randomization) was removed from Version 6.0 of this protocol. |
|---------------------------------------|--|
| Key Eligibility Criteria: | Subject must be ≥ 18 years old, have newly diagnosed AML with intermediate or poor risk cytogenetics, have confirmed CR or CRi following completion of intensive Induction and Consolidation chemotherapies, have achieved first CR or CRi (after induction) within 120 days of the first dose of study drug or be no more than 75 days since last dose of intensive conventional (including both Induction and Consolidation) chemotherapies until enrollment, and have an Eastern Cooperative Oncology Group (ECOG) performance status of ≤ 2. The key laboratory requirements are as follows: • creatinine clearance ≥ 30 mL/minute; calculated by the Cockcroft Gault formula or measured by 24-hour urine collection; • bilirubin < 3.0 × upper limit of normal (ULN) (adequate liver function) for Part 1, or bilirubin < 2.0 × ULN for Part 3; • absolute neutrophil count ≥ 1,500/μL; • platelets ≥ 100,000/μL. |
| Study Drug and Duration of Treatment: | Part 1: Venetoclax QD for each 28-day cycle for 24 cycles + AZA QD for 5 days (Days 1 to 5) of each 28-day cycle up to 6 cycles. At investigator's discretion, subjects benefiting from treatment at the end of Cycle 24 may continue on venetoclax for up to 48 cycles. Part 3 (Dose Finding): Venetoclax QD for each 28-day cycle up to 24 cycles + oral AZA QD for 14 days (Days 1 to 14) of each 28-day cycle up to 24 cycles. |
| Date of Protocol Synopsis: | 26 April 2024 |

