- 2 10. Subjects with human immunodeficiency virus (HIV) will be permitted provided that subjects have stable disease and are on antiretroviral medication (highly active antiretroviral therapy [HAART]) that are not strong or moderate cytochrome P450 (CYP)3A inducers. Appropriate dose adjustments for venetoclax will be made for HAART therapy implicated in drug-drug interactions.
- ✓ 11. No subjects with active hepatitis B virus (HBV) and/or hepatitis C virus (HCV) with high viral titers. Subjects with HBV inactive carrier status and/or HCV with low viral titers on antivirals (nonexclusionary medications) are eligible.
- ✓ 12. No known active SARS-CoV-2 infection. If a subject has signs/symptoms suggestive of SARS-CoV-2 infection, they should undergo molecular (e.g., PCR) testing to rule out SARS-CoV-2.

 Note: SARS-CoV-2 diagnostic tests should be applied following local requirements/recommendations. Subjects who do not meet SARS-CoV-2 infection eligibility criteria must be screen failed and may only rescreen once (Section 4.1).
- 13. No cardiovascular disability status of New York Heart Association Class > 2. Class 2 is defined as cardiac disease which subjects are comfortable at rest but ordinary physical activity results in fatigue, palpitations, dyspnea, or angina pain.
- 14. No chronic respiratory disease that requires continuous oxygen or significant history of renal, neurologic, psychiatric, endocrinologic, metabolic, immunologic, hepatic, cardiovascular disease, any other medical condition that, in the opinion of the investigator, would adversely affect his/her participating in this study.
- 15. No malabsorption syndrome or other condition that precludes enteral route of administration.
- 16. No evidence of other clinically significant uncontrolled systemic infection requiring therapy (viral, bacterial, or fungal).
- 2 17. No psychiatric illness/social situation that would limit compliance with the study.
- 18. No history of any malignancy with the exception of:
 - Adequately treated in situ carcinoma of the cervix uteri or carcinoma in situ of breast;
 - Basal cell carcinoma of the skin or localized squamous cell carcinoma of the skin;
 - Previous malignancy confined and surgically resected (or treated with other modalities) with curative intent;

- Prior history of malignancy which is considered to be cured by the investigator.

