6.3 Dose-Limiting Toxicity Criteria

Part 1 (Dose Confirmation) and Part 3 (Dose Finding)

Any of the following events during Cycle 1, which are considered possibly or probably related to the administration of venetoclax, will be considered a DLT:

- Hematologic toxicities
 - any Grade ≥ 3 neutropenia lasting more than 7 days
 - any Grade ≥ 3 thrombocytopenia lasting more than 7 days
- Nonhematologic toxicities
 - any Grade 3 AE lasting ≥ 72 hours except for Grade 3 hypersensitivity reactions or Grade 3 localized injection-site toxicities
 - Grade ≥ 3 nausea, diarrhea, or vomiting despite adequate/maximal medical intervention lasting more than 7 days (Part 3 only)
 - any Grade ≥ 4 AE
 - any Hy's law cases defined as elevated aspartate aminotransferase (AST) or alanine aminotransferase (ALT) ≥ 3 × ULN with concurrent elevated total bilirubin ≥ 2 × ULN in the absence of elevated alkaline phosphatase or other conditions that could cause these laboratory abnormalities

In addition, AEs not meeting above criteria but lead to omitting > 20% of the scheduled dose within the cycle should be considered as a DLT unless clearly related to underlying disease.

Treatment delay due to toxicity lasting greater than 14 days since the last dose of venetoclax will also be considered DLT.

Any DLT will require an interruption and possible discontinuation of venetoclax or AZA. Venetoclax may be reintroduced at a reduced dose if the toxicity grade returns to ≤ Grade 1 or to baseline if Grade 2 at study entry. If the subject is considered to be acceptable for resumption of venetoclax dosing at the same dose or reduced dose on Day 7 of the dose interruption, the event should not be designated as a DLT.

To be considered DLT-evaluable in Part 3, subjects must complete at least 80% of assigned venetoclax dosing and oral AZA dosing in Cycle 1 or experience a DLT in Cycle 1.

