9.3 Analysis of Laboratory Data

Unless otherwise specified, analysis of laboratory data will include post-baseline measurements within 30 days of the last dose of the study drug for Arm A or Part 1 or within 30 days of the end of Cycle 24, disease relapse, or study discontinuation whichever is the earliest for subjects in Arm B.

Data collected from central and local laboratories, including additional laboratory testing due to an SAE, will be used in all analyses. The clinical laboratory tests defined in the protocol operations manual (e.g., hematology and clinical chemistry) will be summarized. Change from baseline will be summarized and presented for each lab test at scheduled post-baseline visits defined in Appendix C. Baseline is defined as the last non-missing observation before the first administration of study drug or randomization if no study drug is given.

For shifts relative to National Cancer Institute Common Toxicity Criteria for Adverse Events (NCI CTCAE version 4.03), baseline and post-baseline laboratory observations will be categorized as grade 0, grade 1, grade 2, grade 3, or grade 4 according to NCI CTCAE grade version 4.03. The baseline grade is defined as the grade of the last measurement collected on or prior to the first dose of study drug (or randomization for non-treated subjects). In cases where multiple values are collected on the same day, the maximum grade value will be selected as the value for that day. The maximum NCI toxicity grade value is the value with highest NCI toxicity grade collected after the first dose of study drug.

For each lab test, cross tabulate will be generated for the number of subjects with baseline values of grade 0, grade 1, grade 2, grade 3, grade 4, or missing grade versus maximum post-baseline values of grade 0, grade 1, grade 2, grade 3, grade 4, or missing grade. All subjects in the safety analysis set will be included in the cross tabulation regardless whether baseline or post-baseline measurements are collected.

The separate laboratory shifts tables based on the two criteria below will be generated for each laboratory tests related to CTCAE:

- 1. Shifts from grade 0 (normal) at baseline to grade 1 4 post-baseline (maximum) and worsening from an abnormal baseline value of at least one grade up post-baseline (maximum)
- 2. Shifts from grade 0 2 at baseline to grade 3 or 4 post-baseline (maximum) and from grade 3 at baseline value to grade 4 post-baseline (maximum).

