For above shift tables, baseline grade of 0 (normal) will be imputed for all subjects with at least one post-baseline but missing a baseline value for each lab test.

[figure not shown]
Detailed listings of all data for subjects experiencing NCI CTCAE grade 3 to 4 blood chemistry and hematology values will be provided.

DILI will be assessed using laboratory data, including alanine aminotransferase (ALT), aspartate aminotransferase (AST) and total bilirubin (TBILI), based on Hy's law criteria. Number and percentage of subjects with liver enzyme value meeting the Hy's law criteria for potential drug-induced liver injury (ALT $> 3 \times$ ULN or AST $> 3 \times$ ULN and TBILI $> 2 \times$ ULN within 72 hours of each other) will be presented.

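### SAP 9.3 counts Hy's law cases on fixed ULN multiples with no baseline reference, so a Part 1 subject with unchanged entry values can be tabulated as potential drug-induced liver injury

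*Protocol*

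**What the plan says.** **Entry.** The Protocol Synopsis and Section 5.1, criterion 3, give the same limits: "bilirubin < 3.0 × upper limit of normal (ULN) (adequate liver function) for Part 1, or bilirubin < 2.0 × ULN for Part 3". The only other laboratory limits are for creatinine clearance, neutrophils and platelets. Neither part has an AST or ALT limit. Beyond that, hepatic screening rests on the hepatitis B/C criterion and on investigator judgement, which includes "significant history of renal, neurologic, psychiatric, endocrinologic, metabolic, immunologic, hepatic, cardiovascular disease" (criterion 14).

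**SAP table.** Section 9.3 will report the "Number and percentage of subjects with liver enzyme value meeting the Hy's law criteria for potential drug-induced liver injury". The rule is ALT or AST above 3 × ULN, with bilirubin given as "ULN and TBILI $> 2 \times$ ULN within 72 hours of each other". On timing, "analysis of laboratory data will include post-baseline measurements within 30 days of the last dose of the study drug". No baseline value enters the rule, and subjects already abnormal at entry are not set apart.

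**DLT definition.** Protocol Section 6.3 has its own Hy's law item: "elevated aspartate aminotransferase (AST) or alanine aminotransferase (ALT) ≥ 3 × ULN with concurrent elevated total bilirubin ≥ 2 × ULN". It applies "in the absence of elevated alkaline phosphatase or other conditions that could cause these laboratory abnormalities". Like every item in that list, it also requires the event to be attributed to venetoclax and to fall in Cycle 1.

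**The concern.** A count labelled as potential drug-induced liver injury should separate liver tests that went wrong on treatment from those that were abnormal before the first dose. In Part 1 the entry limit for bilirubin lies above the Hy's law cut-off and transaminases are not capped, so both limbs can be met before any drug is given. The first post-baseline sample then makes the subject a case without any change.

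Hy's law cases are usually few, and each one is read closely. If the table cannot show whether a case was new, a reader of the study report may see a liver signal that was present at entry. A real case in a subject with a high baseline is equally hard to recognise from the count alone.

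The same SAP section is baseline-referenced elsewhere. Its two laboratory shift tables classify subjects by movement from baseline grade. The SAP also expects hepatic impairment at entry: it defines it (Appendix F), tabulates it (Section 7.1) and uses it as a safety subgroup (Section 9.4). That subgroup analysis covers the adverse events of Section 9.2 only and does not reach the Hy's law count.

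**Working it through.** The plan states no figure on this point, so there is none to reproduce. The check applies the written rules to subjects whose values do not change after entry.

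**Inputs**
- Entry bilirubin: below 3.0 × ULN in Part 1, below 2.0 × ULN in Part 3 (Synopsis; Section 5.1, criterion 3).
- Entry AST/ALT: no limit (same places).
- SAP rule: ALT or AST > 3 × ULN and bilirubin > 2 × ULN (SAP 9.3).
- Laboratory limb of the DLT item: AST or ALT ≥ 3 × ULN and bilirubin ≥ 2 × ULN (Section 6.3).
- Part 1 enrolment: 66 (Synopsis; Section 4.1).

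**Step 1. Unchanged values (all in multiples of ULN)**

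| Part | Bilirubin | ALT | SAP 9.3 rule met | Section 6.3 laboratory limb met |
|---|---|---|---|---|
| 1 | 2.5 | 4 | yes | yes |
| 1 | 2.5 | 3 | no | yes |
| 1 | 2.0 | 4 | no | yes |
| 1 | 2.5 | 1 | no | no |
| 1 | 1.99 | 4 | no | no |
| 3 | 1.99 | 4 | no | no |

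No laboratory entry criterion excludes any of these subjects. The first row is the problem: no change on treatment, and a case in the SAP table. Rows two and three show the effect of the different inequality signs. The last column is the laboratory limb only, before the attribution and other-cause conditions.

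**Step 2. One limb already met.** A Part 1 subject at bilirubin 2.5 with normal transaminases needs no bilirubin rise; a transaminase rise alone completes the rule. Such a case may be real injury and should not be called false. It does need to be identifiable.

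**Step 3. Part 3.** Entry bilirubin is below 2.0, so unchanged values meet neither rule. A subject at 1.9 with high transaminases needs a bilirubin rise of 2/1.9 = 1.05-fold, which is small but still a change. The SAP supplied is written for protocol version 2.0 (Parts 1 and 2) and does not cover Part 3.

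**Step 4. Size of one case.** 1/66 = 1.5 percentage points in Part 1 overall. SAP 9.1 also presents Part 1 safety by dose level; in a cohort of 20 it is 1/20 = 5.0 points.

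**Step 5. The two definitions side by side**

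| Feature | SAP 9.3 | Protocol 6.3 |
|---|---|---|
| Inequality | > | ≥ |
| Timing of the two limbs | within 72 hours | concurrent, no interval given |
| Alkaline phosphatase and other causes | not mentioned | must be absent |
| Attribution to venetoclax | not required | required |
| Baseline term | none | none |

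**Step 6. Grouping.** The SAP joins ALT, AST and bilirubin by an *or* followed by an *and*, without brackets. Under the usual programming order (*and* before *or*), ALT > 3 × ULN alone would qualify. That is unlikely to be meant, but it is what the expression allows.

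**The case against.** The strongest defence is that this table is a deliberately broad laboratory screen. The SAP calls the injury potential, and a screen that reviewers then examine case by case may include pre-existing abnormality. A screen and a causality-gated DLT serve different purposes, so a subject who appears in one and not the other is not in itself a contradiction. Section 9.3 also gives change from baseline and a baseline-by-worst-grade cross-tabulation for each test, and investigators may exclude relevant hepatic disease at entry.

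Much of this stands, and it is why the fixed-ULN count should be kept. It does not remove the gap. The cross-tabulations are per test and in aggregate; they do not show whether the subjects in the Hy's law count are those who were abnormal at entry. Investigator judgement on hepatic history is not a transaminase limit.

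A reader might go further and infer that pre-existing elevation inflates the primary endpoint, for example by moving a Part 1 cohort from 3/20 (15%) to 4/20 (20%) and across the 20% rule. The documents do not support that. Section 6.3 requires attribution to venetoclax and the absence of another explanation, so an unchanged pre-dose abnormality has two ways out, by judgement if not by a baseline rule. DLTs are confined to Cycle 1, and nothing in the documents makes the SAP table a source for the DLT count.

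**Conclusion.** The point holds for one output: the Part 1 Hy's law count in SAP 9.3. As written, that count can include a subject whose liver values did not change from entry, and it does not distinguish such a subject from a new case. Each one adds 1.5 percentage points among 66.

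How many subjects this involves cannot be said. A reader might want an expected number of false cases, but the documents give no distribution of entry bilirubin or transaminases. Any figure would rest on invented frequencies, and counting every later transaminase rise in a subject with high entry bilirubin would label possible real injury as false.

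The conclusion rests on the current protocol's Part 1 entry limits and on the SAP supplied. It does not extend to the DLT endpoint or, for unchanged values, to Part 3. The differences between the SAP and Section 6.3 definitions stand however common baseline elevation is. This is a modest, cheap correction to a safety table, not a threat to the dose decision.

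**What to change.** In SAP 9.3:

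1. Keep the fixed-ULN count as the sensitive screen.
2. Beside it, report the cases by baseline liver status. For each limb (transaminase, bilirubin), show whether the cut-off was already met at baseline or newly met afterwards, with missing baseline as its own category.
3. List baseline and post-baseline ALT, AST, bilirubin and alkaline phosphatase for every case.
4. Bracket the expression: (ALT > 3 × ULN or AST > 3 × ULN) and total bilirubin > 2 × ULN.
5. Reconcile the inequality signs, the timing, and the alkaline phosphatase and other-cause clause with Protocol Section 6.3, or state that the differences are intentional and why.

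No change to the entry limits or to the DLT rule is proposed. A baseline multiple should not replace the present count: the documents supply no threshold, and a replacement could hide a true case in a subject with a high baseline.

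The cost is one table split and one listing. Protocol Appendix H schedules clinical chemistry at screening, on Cycle 1 Day 1 and after baseline. The test panel itself is not in the documents supplied, so it is assumed to contain these four tests, all of which Section 6.3 already relies on. Protocol Section 7.1 has the SAP finalised before database lock, so the text can be changed up to that point.
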